#### **Model Development and Performance Assessment**

### General Modeling Approach

To generate a risk prediction model, the relative contribution of the clinical and genetic predictors was quantified by using a competing risk model for SCD events with non-SCD death as the competing risk. This analysis was implemented by using cause-specific regression. To ensure that the quantification was pertinent to the clinical context, patients were administratively censored at 5 years from first evaluation. Two models were considered: a clinical-only model and a clinical/genetic model that included genotype status of the patient. Patients harboring a pathogenic/likely pathogenic causal variant on genetic testing, that is, genotype-positive patients, were compared with patients without a causal variant on testing. We applied a model-boosting algorithm to the cause-specific hazard regression to identify and quantify the association between the candidate risk factors and the composite outcome. For continuous risk factors, the associations were modeled without the assumption of linearity using penalized b-splines. The estimated nonlinear associations were summarized graphically. On the fitting of the 2 boosted models, we then obtained the linear predictors and baseline hazard for the SCD events.

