3. DATA COLLECTION

3.1 Specific data fields for the initial retrospective review

We will be collecting information on:

- *Screening and demographics*: Variables include eligibility screening and basic demographics such as month/year of birth and gender.
- *Medical history, family history, cardiac work-up*: This information will be captured at the time of first evaluation of HCM (+/-12 months), last reported evaluation and event driven. Events include death, transplant, SCD, aborted SCD, mechanical circulatory support, cardiac surgery, device implantation (e.g. ICD). Data variables to be collected include family history of HCM and sudden cardiac death, history of syncope & history of aborted SCD. Cardiac imaging (echo, cMRI) & other cardiac tests (Holter, exercise) measurements will be captured along with date of test. Management recommendations including exercise restrictions and prescribed medications will also be collected.
- *Genetic testing*: Results of clinical genetic testing will be captured including test used, gene affected and familial inheritance.

Please refer to appendices for detailed case report forms.

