# PRecIsion Medicine in CardiomyopathY (PRIMaCY)

Statistical Analysis Plan

July 21, 2020

All statistical analyses were performed using R version 3.4.1 with survival, multiple imputation by chained equations, mboost, riskRegression, and mlr packages. Clinical characteristics were summarized using descriptive statistics. Continuous variables were summarized using median and interquartile range, whereas categorical variables were summarized using frequencies and proportions. The primary outcome was time to an SCD event during 5-year follow-up defined as a composite outcome of SCD, resuscitated sudden cardiac arrest (including sustained VT/ventricular fibrillation), and aborted SCD events, that is, appropriate shock in a patient with a primary prevention ICD. Event-free survival was estimated by using the Kaplan-Meier method as was the cumulative proportion of SCD events over time.

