### Model Tuning

To tune the boosting model, we applied 10 repeated 4-fold cross-validations to determine the hyperparameter of the boosting model. In this exercise, we considered a small learning rate (step size) of 0.01 and a large number of steps. Within each cross-validation iteration, we imputed the missing values by using multiple imputation by chained equations before training the model. The plausibility of missing at random assumed in the imputation depends on the candidate risk factors. As long as the candidate risk factors considered in the study are comprehensive, as in our study, this assumption is reasonable. Next, we applied the trained model and calculated the c-statistic on the cross-validation data for each step. The optimal number of steps (ie, the value of the boosting model hyperparameter) was the one that maximized the c-statistic averaged over all cross-validation iterations. The final model was then fitted using all data with the optimal hyperparameter value estimated in the model-tuning exercise. Given the competing risk data, separate cause-specific hazard regression models were fitted and tuned: 1 for SCD events and the other for non-SCD deaths. Because of a small number of patients with non-SCD deaths, we only applied 3-fold cross-validation to identify and quantify the risk factors associated with non-SCD deaths.

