### Model Performance

On model fitting, both prognostic index and the 5-year cumulative proportion of SCD events were quantified for each patient. The discriminatory power of the final model was quantified using the c-

statistic for competing risk models. Model calibration was assessed by stratifying patients into 3 risk groups based on tertiles of the predicted 5-year probability of a SCD event and by creating a calibration curve to show the relationship between the observed and predicted 5-year probability of events.

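### Heart transplant is recorded as an event but has no place in the competing-risk model; if transplanted children are censored, the predicted 5-year SCD risk would be overstated, slightly on average and more where transplant is likely

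*SAP*

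**What the plan says.** **Outcome.** The SAP's opening section states: "The primary outcome was time to an SCD event during 5-year follow-up defined as a composite outcome of SCD, resuscitated sudden cardiac arrest", together with appropriate shocks from a primary-prevention ICD. Transplant is not part of it.

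**Competing event.** General Modeling Approach specifies "a competing risk model for SCD events with non-SCD death as the competing risk". Model Tuning leaves no room for a third event type: "separate cause-specific hazard regression models were fitted and tuned: 1 for SCD events and the other for non-SCD deaths". It adds: "Because of a small number of patients with non-SCD deaths, we only applied 3-fold cross-validation".

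**Censoring.** The only rule given is that "patients were administratively censored at 5 years from first evaluation".

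**Product.** Under Model Performance, "both prognostic index and the 5-year cumulative proportion of SCD events were quantified for each patient".

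**Transplant.** Protocol section 3.1 lists it beside death, not within it: "Events include death, transplant, SCD, aborted SCD, mechanical circulatory support, cardiac surgery, device implantation (e.g. ICD"). The word transplant does not occur in the SAP.

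**The concern.** The calculator delivers an absolute risk. Unlike a hazard ratio, an absolute 5-year risk depends on every event that takes a child out of risk before year 5. The SAP accepts this by modelling non-SCD death as competing. Transplant removes the diseased heart, so it ends the risk of a native-heart SCD event just as non-SCD death does. It is nevertheless left out of the competing event, and nothing states how it is handled.

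Two things are at stake. First, Protocol section 6 expects the score to inform decisions for individual patients, so an error that grows with a child's own transplant risk matters more than its cohort average suggests. Second, the planned checks may not show it. If observed risk in the calibration curves is computed with the same coding as predicted risk, in the development cohort or the replication cohort, both sides carry the same error and agree. The descriptive estimate has the same gap: "Event-free survival was estimated by using the Kaplan-Meier method as was the cumulative proportion of SCD events over time", again with no rule for transplant.

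**Working it through.** **1. The plan's own figure.** Protocol section 5 gives no transplant rate. It anticipates 3,000 screened, 70-80% eligible, a 6% SCD event rate and 100-150 events.
- 3,000 × 0.70 × 0.06 = 126
- 3,000 × 0.80 × 0.06 = 144

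Both lie inside the stated range, although its ends correspond to 100/0.06 ≈ 1,667 and 150/0.06 = 2,500 eligible children rather than 2,100 and 2,400. Nothing below depends on this. The 6% is used only as an illustrative 5-year SCD risk; the Protocol does not attach a time horizon to it.

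**2. Handlings the SAP leaves open.** A transplanted child could be (a) censored at transplant, (b) kept under follow-up to year 5, or (c) counted with the non-SCD deaths. Handling (c) would be sound, but it is not what the text says. Handlings (a) and (b) are worked through below.

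**3. Handling (a), censored at transplant.** *Assumptions:* constant cause-specific hazards over 5 years; net 5-year risks (the risk if no other event could occur) of 6% or 15% for SCD, 1% for non-SCD death and 2-30% for transplant. The 15%, the 1% and all transplant values are assumptions.

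Hazards: h = −ln(1 − p)/5 for SCD (hS), death (hD) and transplant (hT).

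SCD risk with transplant censored: hS/(hS + hD) × [1 − exp(−5(hS + hD))].

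SCD risk with transplant competing: hS/(hS + hD + hT) × [1 − exp(−5(hS + hD + hT))].

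*Example, 6% SCD and 10% transplant:* hS = 0.01238, hD = 0.00201, hT = 0.02107.
- Censored: 0.8603 × (1 − 0.94 × 0.99) = 0.8603 × 0.0694 = 5.97%
- Competing: 0.3490 × (1 − 0.94 × 0.99 × 0.90) = 0.3490 × 0.1625 = 5.67%
- Excess: 0.30 points; 5.97/5.67 − 1 = 5.3%

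| Assumed net transplant risk | 6% SCD: censored → competing | Excess (points) | Relative excess | 15% SCD: censored → competing | Excess (points) |
|---|---|---|---|---|---|
| 2% | 5.97 → 5.91 | 0.06 | 1.0% | 14.93 → 14.78 | 0.15 |
| 5% | 5.97 → 5.82 | 0.15 | 2.6% | 14.93 → 14.56 | 0.37 |
| 10% | 5.97 → 5.67 | 0.30 | 5.3% | 14.93 → 14.19 | 0.74 |
| 20% | 5.97 → 5.36 | 0.61 | 11.4% | 14.93 → 13.42 | 1.51 |
| 30% | 5.97 → 5.03 | 0.94 | 18.6% | 14.93 → 12.62 | 2.31 |

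The relative excess hardly depends on the SCD risk (6-15%) or the death risk (1-2%). It is driven by transplant risk.

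**4. Handling (b), followed on.** Suppose transplanted children stay in the risk set, have no further SCD event and die at the same rate as before. The estimated SCD hazard is then hS multiplied by the share of those at risk who still have their native heart. Carried numerically through 5 years at 6% SCD, 1% death and 10% transplant, this gives 5.67%, the same as the competing-risk value. There is no overstatement on average. However, the fitted hazard is no longer that of the native heart, and deaths after transplant count as non-SCD deaths of HCM patients in a model the SAP describes as already short of events.

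**The case against.** **The bias is not established.** A reader might infer that the published risks are too high. The documents do not support that. Censoring at transplant is the usual treatment of an event not named as competing in a cause-specific analysis, but the SAP does not state it, and step 4 shows that following children on gives no average excess. This objection stands, and the overstatement is conditional on censoring.

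**The size is assumed.** No transplant rate appears anywhere, overall or by disease severity. At 5% transplant the excess is 0.15 points on about 6%. With 2,100-2,400 children the binomial standard error of a 6% risk is √(0.06 × 0.94/2,100) = 0.52 to √(0.06 × 0.94/2,400) = 0.48 points, so the 95% limits are about ±1 point. The average effect is well inside sampling error. This stands too. It does not remove the point, because a systematic excess does not shrink with sample size and is larger for a child with a high transplant risk. How many such children there are is unknown.

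**The target could be SCD risk in the absence of transplant.** That is a coherent quantity for judging primary prevention, and censoring would suit it. The SAP does not state this target, though, and by treating death as competing it works with real-world absolute risk. This is a partial defence only.

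**The risk-factor associations need not be wrong.** A reader might also infer that they are biased. Given covariates that explain transplant, censoring at transplant does not by itself bias the cause-specific SCD hazard. The error under handling (a) lies in the absolute risk.

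**Data for the recode are not fully shown.** Section 3.1 lists transplant among the event-driven captures but mentions a date explicitly only for tests. A transplant date is likely but inferred. The SAP gives no data fields for the replication cohort.

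**Conclusion.** The point holds in conditional form. The SAP limits the competing event to non-SCD death and fits only two cause-specific models, while the Protocol records a further event that ends the native heart's risk. Both handlings that fit the written text have a defect. Censoring overstates the absolute 5-year risk; following on mixes donor-heart time and post-transplant deaths into the two models.

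Under censoring, constant hazards and the assumed transplant risks, the excess stays under 3% in relative terms up to a 5% transplant risk. It reaches about 5% at a 10% risk and about 11% at a 20% risk. It is therefore small for the cohort as a whole and material only for patients with a high transplant risk, a group the documents do not quantify. This is a cheap improvement that does not put the model as a whole in doubt.

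**What to change.** 1. In General Modeling Approach and Model Tuning, define the competing event as non-SCD death or heart transplant, whichever comes first, and end follow-up at transplant.
2. Refit and retune the competing-event model on this combined event. If post-transplant time had been included, refit and retune the SCD model as well, because its risk set changes.
3. Use the same coding for observed risk in the calibration curves, and in the replication cohort where transplant is recorded there.
4. State how transplant was handled in the existing analysis, report the number of transplants within 5 years, and compare predicted risks under the two codings.

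**Cost.** One recode of an event the Protocol already collects (assuming its date was captured) and one or two refits. The downsides are a competing event of mixed kind and, if transplant had been censored, slightly lower predicted SCD risks. If the transplant count turns out to be very small, the comparison in step 4 will show that little changes.

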1.2 BACKGROUND

Hypertrophic cardiomyopathy (HCM) is a commonly inherited heart muscle disease, which can present in childhood, adolescence or adulthood. It accounts for 42% of childhood cardiomyopathy and has an incidence of 0.47/100,000 children¹. It is a frequent cause of sudden cardiac death (SCD) with those aged between 8-16 years at highest risk^{2,3}.

For adults with HCM, identified risk factors for SCD include non-sustained ventricular tachycardia (VT)^{4,5}, left ventricular (LV) hypertrophy (>3cm)⁶ presence of LV outflow tract obstruction⁷, family history of sudden death², and hypotensive response of blood pressure on exercise testing⁸.

However, the risk factors are less clear in the pediatric population. Historically along with the risk factors listed above, myocardial bridging was thought to be associated with a poor outcome in children with HCM⁹. Other screening tools have included the use of ECG measurements of R and S wave height on ECG along with septal hypertrophy by echocardiogram to predict those at risk for SCD¹⁰. HCM is inherited in an autosomal dominant pattern, the most frequently encountered HCM-associated mutations occur in MYH7 and MYBPC3 genes. To date no correlation has been found between specific genotype and outcome in patients with HCM¹¹. Loar *et al* reported a significant increase in ventricular hypertrophy in genotype positive patients¹². As LV wall thickness remains one of the SCD risk factors in adults, one could postulate therefore that being genotype positive may increase the risk of SCD. Analysis of data from SickKids Hospital (Toronto, ON) in pediatric HCM revealed that mutations in MYH7 gene and a higher number of pathogenic mutations in one or more genes were associated with a higher incidence of major adverse cardiac events¹³. Emerging imaging tools such as Cardiac MRI to determine the presence of Late Gadolinium enhancement may also predict those who have developed myocardial fibrosis and are at risk for SCD^{14,15}.

The European Society of Cardiology (ESC) recently published guidelines on the diagnosis and management of HCM in adults¹⁶ which led to the development of a clinical risk calculator to predict the risk of SCD at 5 years in adults >16 years old¹⁷. This model uses age, maximum LV

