2.2 SUBJECT SELECTION

2.2.1 Inclusion Criteria

HCM patients ≤ 18 years of age at first presentation will be included. This includes phenotype positive patients, and phenotype negative gene positive patients considered at risk. Phenotype positive patients are patients with a clinical diagnosis of HCM based on signs, symptoms, family history, EKG and/or echocardiographic features (septal or LV posterior wall thickness z-score (PWd) > +2.0 or ratio of hypertrophied region to PWd > 1.3 in the absence of anatomic LVOT obstruction) of HCM.

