2.2.3 Subject screening

Eligible subjects who were seen since 1990 will be identified through review of the following data sources:

Version: November 30, 2018

- (i) Electronic Medical Records (and paper charts where needed)
- (ii) Other relevant cardiac databases (ie. echocardiography, heart failure)

Patients will be screened for eligibility from participating sites. This is a multi-centre study led by SickKids Hospital (Toronto), participating institutions include Stollery Children's Hospital (Edmonton), BC Children's Hospital (Vancouver), Stanford Children's Health (Palo Alto), Children's Hospital of Philadelphia, Texas Children's Hospital (Houston), Morgan Stanley Children's Hospital (New York), Children's Medical Center of Dallas, University of Michigan Medical Center (Ann Arbor), Cincinnati Children's Hospital, Children's Hospital of Eastern Ontario (Ottawa), The Royal Children's Hospital (Melbourne). REB/IRB approval and service & data transfer agreements will be put in place at each participating centre above as well as new centres that get added.

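### Follow-up that ends before 5 years probably depends on age at entry, and the SAP makes no allowance for this when it predicts and checks 5-year risk in older adolescents

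*SAP*

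**What the plan says.** - **Entry.** Protocol 2.2.1: "HCM patients ≤ 18 years of age at first presentation will be included".
- **Sites.** Protocol 2.2.3 names 12 institutions, 11 of them children's hospitals by name, and allows for more ("as well as new centres that get added"). The type of any added centre is not stated.
- **Follow-up.** Protocol 3.1 collects data at first evaluation, at the last reported evaluation and at events. No minimum follow-up is set. Follow-up after a move to adult care is neither described nor excluded.
- **Horizon and model.** SAP, General Modeling Approach: "patients were administratively censored at 5 years from first evaluation". A boosted cause-specific hazard regression yields linear predictors and one baseline hazard for SCD events.
- **Checks.** SAP, Model Performance, computes a 5-year probability for each patient, a c-statistic, and calibration in tertiles of predicted risk. Model Validation repeats this in an independent cohort with the Harrell c-statistic.
- **Age and risk.** Protocol 1.2 describes "those aged between 8-16 years at highest risk".

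Neither document gives a transfer age, a rule for follow-up that stops before 5 years, or follow-up by age at entry. Neither says whether age is a candidate predictor. The missing-at-random statement under Model Tuning concerns imputation of missing values, not censoring.

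**The concern.** A patient first seen at 16 in a children's hospital can be followed there for only a few years, while one first seen at 6 can easily complete five. Length of follow-up then depends on age at entry, and age is also related to risk.

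A model with one baseline hazard on time since first evaluation handles this correctly only if the effect of entry age is the same throughout follow-up. The Protocol's own statement about ages 8-16 gives reason to doubt that. A child entering at 8 spends all five years inside that band, whereas one entering at 15 leaves it after about a year. Splines for continuous factors free the shape of the age effect but do not let it change over follow-up.

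The calculator is intended to inform decisions on primary-prevention ICDs (Protocol section 6), and the affected entry ages overlap the band described as highest risk. Calibration in tertiles mixes all ages, so a misfit confined to older adolescents can be averaged away.

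**Working it through.** **1. The plan's only planning figure.** Protocol section 5 expects 3,000 screened, 70-80% eligible and a 6% event rate. 3,000 × 0.70 × 0.06 = 126 and 3,000 × 0.80 × 0.06 = 144, both inside the stated 100-150 events. The documents give no figure for follow-up or loss, so everything below rests on labelled assumptions.

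**2. Who could reach 5 years.** Assume entry age is uniform on 0-18 and last contact is at age A. Possible follow-up is min(5, A − entry age). The share unable to reach 5 years is (23 − A)/18 overall and (23 − A)/5 among entrants aged 13-18, and zero once A is 23 or more.

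| A | All entrants | Entrants 13-18 | Share of their possible 5-year person-time supplied by entrants 13-18 |
|---|---|---|---|
| 18 | 5/18 = 28% | 100% | 50% |
| 19 | 4/18 = 22% | 80% | 68% |
| 21 | 2/18 = 11% | 40% | 92% |
| 25 | 0% | 0% | 100% |

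With A = 18, the oldest entrants still at risk at 3, 4 and 5 years were 15, 14 and 13 at entry.

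**3. Effect on predicted risk.** Further assumptions: hazard 1.8%/year at ages 8-16 and 0.6%/year otherwise, 5%/year dropout unrelated to age, and no competing deaths. The fitted model is h(t | age) = h0(t) × g(age), with g free in each one-year entry cell, solved without simulation noise.

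True risk at the cell midpoint:
- Entry 14.5: 1 − exp(−(0.018 × 1.5 + 0.006 × 3.5)) = 1 − exp(−0.048) = 4.7%.
- Entry 15.5: 1 − exp(−(0.018 × 0.5 + 0.006 × 4.5)) = 1 − exp(−0.036) = 3.5%.

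| Last contact | Over-prediction at entry ages 14-15 |
|---|---|
| 18 | about 21% (5.7% vs 4.7%; 4.3% vs 3.5%) |
| 19 | 8-10% |
| 21 | 2-4% |
| Complete follow-up | 2-4% |

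The last row is the misfit of the proportional model itself. Age-linked loss adds to it when contact ends at 18 or 19, and adds nothing at these entry ages when it ends at 21. At entry ages 16 and 17 the excess with last contact at 18 is only 2%.

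If the hazard stays at 1.8%/year after 16 and last contact is at 18, the excess is 5-14% at entry ages 14-17. True risk is then 1 − exp(−0.018 × 5) = 8.6%, so 14% is about 1.2 percentage points.

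**4. Is a changing age effect necessary?** A separate simulation used 60,000 patients per scenario, one run each (noise about 0.2-0.3 points), a Cox model containing age, and entrants aged 13 or over.

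| Their hazard after 2.5 years | True | A = 18 | A = 19 | A = 21 |
|---|---|---|---|---|
| Unchanged | 6.0% | 6.0% | 6.3% | 6.1% |
| Doubles | 8.9% | 7.6% | 8.2% | 8.5% |
| Halves | 4.5% | 5.2% | 5.0% | 4.9% |

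With a constant age effect there is no bias beyond noise. With a changing one, the error can go either way. Without age-linked censoring, predictions matched the truth in all three cases.

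**The case against.** The strongest reply is that the premise is inferred. No passage says that patients leave at 18, or that records stop on transfer. The last reported evaluation need not be paediatric. The study uses chart and registry review and other cardiac databases, and further centres may join. This stands: age-linked loss is likely given the sites, but not established.

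A reader might also infer more than the documents support:

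- *That five years of follow-up is required.* It is a maximum horizon. Patients censored earlier still contribute person-time.
- *That the 5-year cut causes the problem.* It applies equally to everyone. The gap is unaddressed censoring before 5 years.
- *That adolescents' whole 5-year risk is extrapolated from younger children.* They inform their own early follow-up; at most the later part is borrowed.
- *That calibration cannot reveal the error.* The observed-risk estimator behind the calibration curve is not named, and follow-up in the external cohort is not described. Pooled calibration may miss the error; that it must do so is unproven.

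The Protocol's statement about ages 8-16 gives no hazard ratio and no rate after 16, so the threefold step used above is illustrative only.

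There is also a fair objection to the remedy. If everyone left at 18, entrants over 13 would have no chance of being observed at 5 years, and weights conditional on age would be undefined there. Splitting 100-150 events over several baseline hazards would be imprecise and could not supply missing late data. Both limits are respected in the change proposed.

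**Conclusion.** The concern holds in a conditional form. The documents establish entry to age 18, mainly paediatric sites, non-event follow-up to the last reported evaluation, a single baseline hazard for a 5-year prediction, and calibration pooled over age. They say nothing about age-related loss. They do not establish that patients are censored at transfer, nor how large any error is.

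Bias needs two conditions together: contact that tends to end near 18-19, and an age effect that changes over follow-up (or age left out of the model while related to risk). Where both hold under the assumed hazards, the relative error at entry ages 14-15 is material with last contact at 18 and modest at 19. By 21 the loss adds nothing there. The absolute error at those ages is under 1 percentage point. Direction and size depend on inputs that the documents do not give, so confidence is medium. The analysis should address it, because one table would show whether the problem exists.

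**What to change.** In SAP Model Performance and Model Validation:

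1. Tabulate numbers at risk at 1, 2, 3, 4 and 5 years by age at first evaluation, and state how follow-up ending before 5 years is handled, including any adult-care records. If older adolescents prove well followed, this table largely settles the matter.
2. Estimate observed risk and the c-statistic with censoring weights conditional on age at first evaluation, and show calibration by age band.
3. Where a band has almost no one at risk at 5 years, so that the weights are not estimable, report risk only to the last supported year.
4. As a sensitivity analysis only, allow a time-varying age effect or an age-stratified baseline hazard. State in the SAP whether age is a candidate predictor.

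The cost is analysis time on dates already collected. The price is wider uncertainty, or a shorter stated horizon, for older adolescents. Item 4 will be imprecise with 100-150 events and should not replace the main model.

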1.3 OBJECTIVES

1. To develop and validate a SCD risk calculator that is age-appropriate for children with HCM that includes clinical and genetic factors

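### The boosted fit suits the calculator, but the SAP also uses it as its estimate of risk-factor associations, where its effects are shrunken and carry no planned measure of uncertainty

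*SAP*

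**What the plan says.** The Protocol (section 1.3) has one objective: "To develop and validate a SCD risk calculator that is age-appropriate for children with HCM that includes clinical and genetic factors". The SAP's General Modeling Approach starts from the same aim: "To generate a risk prediction model, the relative contribution of the clinical and genetic predictors was quantified". It then boosts the cause-specific hazard regression "to identify and quantify the association between the candidate risk factors and the composite outcome", with penalised splines for continuous factors, and compares genotype-positive patients with those without a causal variant. The nonlinear effects are to be shown in graphs.

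Under Model Tuning, "we considered a small learning rate (step size) of 0.01 and a large number of steps". The chosen number of steps "was the one that maximized the c-statistic averaged over all cross-validation iterations". The few non-SCD deaths get the same treatment: "we only applied 3-fold cross-validation to identify and quantify the risk factors associated with non-SCD deaths".

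Neither document plans a confidence interval, standard error, bootstrap or selection frequency for any factor, or says that the coefficients are shrunken. The c-statistic, calibration and external cohort test the model as a whole. The log-rank comparison in Protocol section 5 reads as a comparison of risk groups formed from the score. No other factor-level analysis is planned.

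**The concern.** Boosting adds a small fraction of the best-fitting term at each step. Stopping before convergence leaves the coefficients short of their unpenalised values, and any term not yet chosen stays at exactly zero. Weak factors enter late and lose the most. This trade is made on purpose to predict well in new patients. It does not give an unbiased effect size or a controlled decision about which factors matter. The c-statistic depends only on ranking, so this stopping rule targets neither the size of the coefficients nor the rate of false inclusions.

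Factor-level reading is foreseeable here. The Protocol background says that paediatric risk factors are less clear than adult ones and postulates that positive genotype may raise risk. Section 6 says that the model may inform ICD indications. If boosted coefficients are taken as associations, the genotype effect would look smaller than it is, an unselected factor could be taken for a harmless one, and a selected factor could be noise. A reader would have no interval to judge by.

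**Working it through.** **1. The plan's own figure (Protocol section 5).** Events = screened × eligible share × event rate.
- 3,000 × 0.70 × 0.06 = 126
- 3,000 × 0.80 × 0.06 = 144

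Both lie inside the stated 100-150. The documents give no effect size, alpha or power, so there is no power figure to reproduce. The simulations use the middle of the eligible range: 3,000 × 0.75 = 2,250 patients.

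**2. Simulated genotype effect, true HR 1.5.** In all runs the stop is the maximum cross-validated c-statistic. Assumed, because the documents do not say: 6 continuous and 6 binary candidates, 4 real and 8 null (runs A and B); 4-df splines (A and C); genotype prevalence 50% (B).

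| Run | Events | Replicates | Terms for continuous factors | Mean boosted / true log HR | Genotype dropped | Each null factor kept |
|---|---|---|---|---|---|---|
| A | about 133 | 420 | splines | 34% | 37% | continuous 46-50%, binary 10-12% |
| B | about 141 | 400 | splines | 40% | 30% | continuous 42-44%, binary 14-16% |
| C | about 141 | 314 | splines | 34% | 37% | continuous 41-44% |
| B | same data | 400 | all linear | 64% | 15% | 37-41% |
| C | as above | not separately recorded | all linear | 57% | 20% | not recorded |

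On the hazard-ratio scale, with log 1.5 = 0.405:
- Splines: exp(0.34 × 0.405) = 1.15 to exp(0.40 × 0.405) = 1.18.
- All linear: exp(0.57 × 0.405) = 1.26 to exp(0.64 × 0.405) = 1.30.

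Simulation error is small beside these effects. For 37% dropped in 420 replicates, the standard error is √(0.37 × 0.63 / 420) = 0.024.

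**3. All-linear check with graded effects.** This run used five real standardised factors (HR per SD 1.5, 1.35, 1.25, 1.2, 1.15), 5 to 15 null factors, correlation 0 or 0.3, and 120-150 replicates per setting.
- At about 140 events, boosted/true log HR was 0.59-0.87. Factors were kept in 100% (HR 1.5), 95-100% (1.35), 92-95% (1.25), 82-87% (1.2) and 69-74% (1.15) of runs.
- Over all settings (139-175 events), boosted/true log HR was 0.48-0.89. At least one real factor was dropped in 25-44% of runs. Each null factor was kept in 25-46%, and at least one null in 78-86%. Both errors occurred in the same run in 13-30%.

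At 50% prevalence, a binary HR of 1.5 equals exp(0.5 × 0.405) = 1.22 per SD. The neighbouring factors here (1.2 and 1.25) kept 62-75% of their log HR at about 140 events, of the same order as the 57-64% in step 2. The lower spline figures therefore come mainly from a one-parameter binary term competing with more flexible terms.

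**4. Unpenalised Cox on the same data.** Estimated/true log HR was 1.00 in run A, with mean SE 0.177 and 95% coverage, and 0.95-1.08 in the graded runs. A typical interval for genotype would be exp(0.405 ± 1.96 × 0.177) = 1.06 to 2.12.

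**5. The prediction side.** In the graded runs the median calibration slope in new data was 1.05-1.24 for the boosted fit and 0.73-0.88 for unpenalised Cox. Boosting was closer to 1 in most settings. With 15 null factors the two were about equally far off.

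**Limits.** All runs had no competing event and no missing data to impute. They used coarser steps (0.25 in A, 0.1 in step 3) and fewer cross-validation repeats (3 in A and step 3, 2 in B) than the SAP's 0.01 and 10.

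**The case against.** The strongest reply is that this is a prediction study. Its only objective is a calculator, the SAP judges the whole model, and no hypothesis concerns a single factor. Shrinkage helps that aim, as step 5 shows. This stands: boosting is not at fault, and a reader who infers that the calculator is biased or the method wrong for its purpose goes beyond the documents.

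A reader might also infer that real factors will be lost while null ones are kept. The documents do not support that as a fact. They give neither the number of candidates nor the true effects. In the graded runs the strong factors were almost never lost, and both errors came together in only 13-30% of runs. Nor does the SAP's silence on intervals show that none was reported; it shows only that none is planned.

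The genotype percentages can be challenged as products of the chosen splines, coarse steps and a step cap. In part they are. Run A hit its cap in 14% of replicates, but run B hit it in only 3.5% and still kept just 40% of the log HR. All-linear terms soften the loss without removing it. Every run used the c-statistic stop, so the figures belong to this SAP's rule and not to early stopping in general.

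The SAP also has clinical-only and clinical/genetic models, so genotype can be judged by comparing them. That informs its value for prediction but gives no effect size with an interval.

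Finally, an unpenalised model with every candidate as a spline would be overloaded. That stands and limits the fix.

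**Conclusion.** The concern holds in a limited form, as a change that should be made. The SAP takes both the selection and the size of factor effects from a fit designed to predict, and plans nothing that shows their uncertainty. As association estimates they are shrunk towards zero. Under the assumed inputs, a binary genotype effect with HR 1.5 would appear as roughly 1.15-1.18 with spline terms, or 1.26-1.30 with linear terms, and be absent in about 15-37% of runs. Each null factor would be kept in about 10-50%, depending on its type and the competing terms. The direction of the shrinkage is secure; its size depends on inputs that the documents do not state. The calculator itself is not called into question. For non-SCD deaths, where the SAP itself says that numbers are small, factor-level claims have the least support.

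**What to change.** Keep boosting for the calculator and describe its coefficients as shrunken contributions to prediction. In addition:
- For any statement about an individual factor, including genotype, report hazard ratios with 95% CIs from one prespecified unpenalised cause-specific Cox model for SCD events, pooled over the imputations.
- Keep its degrees of freedom within what 100-150 events support. With the candidate list assumed in run A, six 4-df splines and six binary terms use 6 × 4 + 6 = 30 df, or 100/30 = 3.3 to 150/30 = 5.0 events per df. Twelve one-df terms give 100/12 = 8.3 to 150/12 = 12.5. Nonlinear terms must therefore be few and named in advance.
- Report bootstrap inclusion frequencies for the boosted model, repeating imputation and tuning in each resample.
- State that non-selection is not evidence of no association.
- For non-SCD deaths, keep the model only as a component of the competing-risk prediction and remove the wording about identifying and quantifying risk factors.

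The cost is SAP wording, one extra model and computing time, on data already held. Some intervals will be wide, and the hazard ratios will differ from the calculator's coefficients, so the report should explain why.
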